6 STUDY PERIODS, TREATMENT REGIMENS AND POPULATIONS FOR ANALYSES

6.1 Study Periods

In all listings, summaries and statistical analyses, the term “**Intended Treatment Period**” will refer to the period from the day of randomization through the day of end of 6-month treatment visit for the subjects who complete 6-month treatment. For subjects who discontinue treatment early:

1. if they complete the 6-month visit, the “**Intended Treatment Period**” will be from day of randomization to the day of the 6-month visit
2. if the subjects do not have the 6-month visit, the “**Intended Treatment Period**” will be from the day of randomization to the earlier of the end date of follow up or intended 6-month treatment for subjects.

This period will be the basis for the summaries of efficacy.

In all listings, summaries and statistical analyses, the term “**Treatment Period**” will refer to the period from the first day of study medication through:

- 2 days after the last dose of study drug when summarizing
- bleeding endpoints

- 30 days after the last dose of study drug when summarizing
 - deaths (as an outcome of an SAE)
 - SAEs
- 2 days (for non-serious AEs) or 30 days (for SAEs) after the last dose of study drug when summarizing
 - overall AEs
 - AEs leading to study drug discontinuation

First dose and last dose of study medication will be defined based on oral anticoagulant and antiplatelet separately. This period will be the basis for the summaries of safety.

In all listings and summaries, the term “**Follow-up Period**” will refer to the period starting the day of the end of treatment visit to the Follow-up visit or phone call which is 30 ± 7 days.

6.2 Treatment Regimens

The Randomized Subjects Data Set will consist of all randomized subjects. In this data set, subjects are categorized to the group to which they were assigned by the IVRS (oral anticoagulant or antiplatelet separately), regardless of the treatment actually received. Efficacy endpoints will be summarized according to the **As Randomized** group.

The Treated Subjects Data Set will consist of all subjects who receive at least one dose of study drug and are categorized to the group to which they are assigned by the IVRS (oral anticoagulant or antiplatelet separately) unless the same incorrect treatment is received throughout the study, in which case the treatment group will be equal to the treatment received. Safety endpoints will be summarized according to the **As Treated** group.

6.3 Populations for Analyses

The following population will be used for the analyses.

Enrolled Population

The Enrolled Subjects population consists of all subjects who signed informed consent.

Randomized Population for analysis can be defined as:

Randomized Population for oral anticoagulant: consists of all randomized subjects who are randomized to oral anticoagulant study drug.

Randomized Population for antiplatelet: consists of all randomized subjects who are randomized to antiplatelet study drug.

In these populations, subjects are categorized according to the **As Randomized** group. The intention-to-treat population of all randomized subjects will be used to analyze all efficacy endpoints.

Treated Population for analysis can be defined as:

Treated Population for oral anticoagulant: is a subset of the Enrolled Population consisting of all subjects who were randomized and received at least one dose of oral anticoagulant study drug.

Treated Population for antiplatelet: is a subset of the Enrolled Population consisting of all subjects who were randomized and received at least one dose of antiplatelet study drug.

When summarizing data using these populations, subjects are categorized to the **As Treated** group.

Evaluable Populations:

is a subset of the *Treated Population for oral anticoagulant* excluding subjects with protocol deviations expected to affect the primary safety endpoint (see [Section 7.2](#)). In the case of treatment assignment error, the data collected up to the start of incorrect treatment will be included.

7 STATISTICAL ANALYSES

7.1 General Methods

All analyses will be performed in SAS[®] using version 9.2 or higher. Unless otherwise stated, all hypothesis tests will be performed using two-sided tests at the 5% significance level.

Continuous variables will be summarized using descriptive statistics including means, standard deviations, minima, maxima and quartiles, and qualitative or discrete variables will be summarized using absolute and relative frequencies.

Time to Event Analyses

Unless specified, calculation of p-values and construction of point estimates and CIs for HR will be based on Cox proportional hazard models. Stratification variables will be included in the model as stratification factors. Additional covariates may be included as described in [Sections 7.5](#) and [7.6](#). Ties will be handled using Breslow's methodology.

Event rates will be estimated and plotted over time using Kaplan-Meier methodology.

Testing Strategy

A hierarchical testing strategy described below will be used to compare the effects of apixaban and VKA between treatment groups.

- Non-inferiority (NI) for the primary endpoint, a composite of ISTH major and CRNM bleeding, will be tested first.
- If NI is not demonstrated, then nominal p-values will be presented for subsequent comparisons between apixaban and VKA
- If NI is demonstrated, then superiority for the composite of ISTH major and CRNM bleeding will be tested. If superiority is not demonstrated, then nominal P-values will be presented for subsequent comparisons between apixaban and VKA.
- If superiority for the composite of ISTH major and CRNM bleeding is demonstrated, then superiority for the composite of all-cause death and all-cause re-hospitalization will be tested. If superiority is not demonstrated, then nominal p-values will be presented for subsequent comparisons between apixaban and VKA.

- If superiority for the composite of all-cause death and all-cause re-hospitalization is demonstrated, then the composite of all-cause death and ischemic events will be tested.

All tests will be performed at the two-sided $\alpha = 0.05$ significance level.

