### Study Assessments and Endpoints

#### Statistical Considerations:

#### Sample Size: 4600

This is a 2 x 2 factorial design with dual primary objectives. The sample size is based on the primary set of comparisons of Apixaban vs VKA for the primary endpoint of ISTH major or CRNM bleeding.

A total of 357 primary endpoint events and 4600 subjects will provide 77% power for test of non-inferiority (NI) using a stratified log rank test of apixaban versus VKA, assuming a NI margin of 1.2, with ISTH major or CRNM bleeding event rates in apixaban and VKA groups of 8.1% per half year and 9% per half year, respectively, one-sided significance level of 0.025, and six month follow up and a 1% per year of loss to follow up. The NI margin was selected because an absolute risk difference of 1.8% (20% of VKA event rate of 9%) in bleeding is considered to be a clinically meaningful difference.

This sample size will also provide at least 77.5% power for superiority test of apixaban versus VKA assuming a risk reduction of 25% and a one-sided significance level of 0.025.

A blinded assessment of the primary endpoint event rate will be performed after 50% of subjects have completed the study. The analyses will focus on the aggregate event rate and the sample size may be increased if the aggregate event rate is lower than anticipated. The blinded event rates will be estimated by an independent statistician not associated with BMS and not otherwise associated with apixaban, and will be provided to the Executive Committee. Sample size may be adjusted (depending on availability of resources) to provide sufficient power for both non-inferiority and superiority test on the primary endpoint and first secondary endpoint. Up to a maximum of 8842 subjects may be randomized to maintain appropriate power for both non-inferiority and superiority test on the

primary endpoint and first secondary endpoint to avoid the potential of futility in this study using the pre- specified rule below:

Sample Size Adjustment for Non-inferiority and Superiority Test on the Primary and Secondary Endpoints				
Observed blinded Event Rate When 50% Patient Complete Tx/half year	Assumed Apixaban Event Rate/half year	Assumed Control Event Rate/half year	# of events	Total Sample Size 80% Power for both NI and superiority
7.6%	0.072	0.08	379	5514
6.65%	0.063	0.07	379	6308
5.7%	0.054	0.06	379	7360
4.75%	0.045	0.05	379	8842

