## 5 STUDY ASSESSMENTS AND PROCEDURES

### 5.1 Flow Chart/Time and Events Schedule

**Table 5.1-1: Baseline and Randomization (CV185316)**

Procedure	Screening/ Randomization Visit	Notes
Eligibility Assessments		
Informed Consent	X	
Inclusion/Exclusion Criteria	X	
Medical History	X	Include assessment of alcohol use, tobacco use, prior VKA use, and CHADS-VASC and HAS-BLED scores
Safety Assessments		
Physical Examination	See Notes	Only if deemed necessary by treating physician. Results of examination will be documented in patient's chart, not on CRF
Vital Signs	X	Blood Pressure and Weight
Assessment of Signs and Symptoms	See Notes	Only if deemed necessary by treating physician. Results of assessment will be documented in patient's chart, not on CRF
Serious Adverse Events Assessment	See Notes	Refer to section 6.1 of the protocol for SAE definitions applying to this study.
Adverse Events Assessment	N/A	
Laboratory Tests	X	Local lab: CBC, chemistry(CHEM7 or equivalent for determination of serum creatinine), coagulation (for PT/PTT/INR) (local lab within 7 days can be used)
Urine Pregnancy Test* ( WOCBP only )	X	*If applicable Serum pregnancy test to be performed only if urine test is positive or un-interpretable
Study Drug		
Randomize	X	
Dispense Study Drug (administer within 24 hours of randomization)	X	Those supplied by BMS or sourced by the investigator

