## 8 STATISTICAL CONSIDERATIONS

### 8.1 Sample Size Determination

This is a 2 x 2 factorial design with dual primary objectives. The sample size is based on the primary set of comparisons between Apixaban vs VKA for the primary endpoint of ISTH major or CRNM bleeding.

A total of 357 primary endpoint events and 4600 subjects will provide 77% power for test of non-inferiority (NI) using a stratified log rank test of apixaban versus VKA, assuming a NI margin of 1.2, with ISTH major or CRNM bleeding event rates in apixaban and VKA groups of 8.1% per half year and 9% per half year, respectively, one-sided significance level of 0.025, six month follow up, and a 1% per year of loss to follow up. The NI margin was selected because an absolute risk difference of greater than 1.8% (20% of VKA event rate of 9%) in bleeding is considered to be a clinically meaningful difference.

This sample size will also provide at least 77.5% power for superiority test of apixaban versus VKA assuming a risk reduction of 25% and a two-sided significant level of 0.05.

A blinded assessment of the primary endpoint event rate will be performed after 50% of subjects have completed the study. The analyses will focus on the aggregate event rate and the sample size may be increased if the aggregate event rate is lower than anticipated. The blinded event rates will be estimated by an independent statistician not associated with BMS and not otherwise associated with apixaban, and will be provided to the Executive Committee. Sample size may be adjusted (depending on availability of resources) to provide sufficient power for both non-inferiority and superiority test on the primary endpoint and first secondary endpoint. Up to a maximum of 8842 subjects may be randomized to maintain appropriate power for both non-inferiority and superiority test on the primary endpoint and first secondary endpoint to avoid the potential of futility in this study using the pre-specified rule below. Table 8.1-1 gives a guideline for sample size adjustment.

Table 8.1-1: Sample Size Adjustment for Non-inferiority and Superiority Test on the Primary and Secondary Endpoints				
Observed blinded Event Rate When 50% Patients Complete Tx/ half year	Assumed Apixaban Event Rate/ half year	Assumed Control Event Rate/ half year	# of events	Total Sample Size 80% Power for both NI and superiority
7.6%	0.072	0.08	379	5514
6.65%	0.063	0.07	379	6308
5.7%	0.054	0.06	379	7360

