5 SAMPLE SIZE AND POWER

A total of 357 primary endpoint events and 4600 subjects will provide 77% power for test of NI using a stratified log rank test of apixaban versus VKA, assuming a NI margin of 1.2, with major or CRNM bleeding event rates in apixaban and VKA groups of 8.1% per half year and 9% per half year, respectively, one-sided significance level of 0.025, six month follow up, and a 1% per year of loss to follow up. The NI margin was selected because an absolute risk difference of greater than 1.8% (20% of VKA event rate of 9%) in bleeding is considered to be a clinically meaningful difference.

This sample size will also provide at least 77.5% power for superiority test of apixaban versus VKA assuming a risk reduction of 25% and a two-sided significant level of 0.05.

A blinded assessment of primary endpoint event rate will be performed after 50% of subjects have completed the study. The analyses will focus on the aggregate event rate and the sample size may

be increased if the aggregate event rate is lower than anticipated. The blinded event rates will be estimated by an independent statistician not associated with BMS and not otherwise associated with apixaban, and will be provided to the Executive Committee. Sample size may be adjusted (depending on availability of resources) to provide sufficient power for both non-inferiority and superiority test on the primary endpoint and secondary endpoint. Up to a maximum of 8842 subjects may be randomized to maintain appropriate power for both non-inferiority and superiority test on the primary endpoint and secondary endpoint using the pre- specified rule below. Table 8.1-1 give a guideline for sample size adjustment.

Table 8.1-1: Sample Size Adjustment for Non-inferiority and Superiority Test on the Primary				
Observed blinded Event Rate When 50% Patients Complete Tx/half year	Assumed Apixaban Event Rate/half year	Assumed Control Event Rate/half year	# of events	Total Sample Size 80% Power for both NI and superiority
7.6%	0.072	0.08	379	5514
6.65%	0.063	0.07	379	6308
5.7%	0.054	0.06	379	7360
4.75%	0.045	0.05	379	8842

Assume time to event follow exponential distribution, 6 months fix follow up, 25% risk reduction for superiority test, and 10 % risk reduction for NI test. Nquery 2.0 and EAST 5.4 are used for the sample size calculation and power calculation of NI and superiority.

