7.6.1 The comparison between apixaban and VKA

7.6.1.1 Analysis of Primary Safety Endpoints

NI and Superiority Tests

All analyses described in this section will be performed on the treated subjects for oral anticoagulant during the treatment period using safety censoring scheme (considering study drugs apixaban/VKA).

The primary objective of the study is to determine if apixaban is NI to VKA for the primary safety endpoint (confirmed ISTH major bleeding and CRNM bleeding). Following the sequential testing strategy outlined in [Section 7.1](#), if non-inferiority for the primary safety endpoint is demonstrated at the one-sided 0.025 significance level then superiority of apixaban relative to VKA for the primary safety endpoint will be tested at the one-sided 0.025 significance level.

The analysis of primary safety endpoint will be performed using a Cox proportional hazard model including oral anticoagulant treatment group (apixaban/VKA) as a covariate and stratified by indication at enrollment (PCI/ACS) and antiplatelet (aspirin/placebo). The treatment effect will be

measured by the estimated HR and two-sided 95% CIs for HR. The non-inferiority will be demonstrated if the upper bound of two-sided 95% CIs for HR is less than 1.2.

The proportional hazards assumption will be checked by examining the plots of the log(-log(survival)) versus survival time for each stratum included in the Cox proportional hazards model.

Interaction between oral anticoagulant (apixaban/VKA) and antiplatelet (aspirin/placebo) is not anticipated, but this assumption will be examined within Cox model including stratification variable indication at enrollment (PCI/ACS), and terms of oral anticoagulant treatment group (apixaban/VKA), antiplatelet (aspirin/placebo), and oral anticoagulant (apixaban/VKA) by antiplatelet (aspirin/placebo) interaction. If quantitative interaction is significant (two sided p-value < 0.1), then qualitative interaction will be assessed using Gail and Simon test (1985)².

Event rates will be estimated and Kaplan-Meier curves will be plotted for the time from first dose of study medication to first occurrence of ISTH major or CRNM bleeding, by treatment group, by treatment group and indication at enrollment (PCI/ACS), and by treatment group and antiplatelet treatment group.

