7.6.2.1 Primary Safety Analysis

The primary safety endpoint will be time to first occurrence of confirmed ISTH major or CRNM bleeding. A point estimate and two-sided 95% CIs for hazard ratio using a Cox proportional hazards model including antiplatelet (aspirin/placebo) as a covariate, stratified by indication at enrollment (PCI/ACS) and oral anticoagulant treatment group (apixaban/VKA) using the treated subjects for antiplatelet during treatment period. A p-value for the test of equality (HR = 1) will be calculated based on the hierarchical testing strategy.

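### The bleeding superiority tests are valid but use no baseline bleeding-risk covariate; pre-specifying variables already scheduled before randomization would probably add a small amount of power

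*SAP*

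**What the plan says.** - **Covariate clause.** SAP 7.1 (Time to Event Analyses) states "Additional covariates may be included as described in" Sections 7.5 and 7.6. The wording is permissive and 7.1 itself lists no covariates.
- **Apixaban versus VKA.** SAP 7.6.1.1 uses a Cox model "including oral anticoagulant treatment group (apixaban/VKA) as a covariate and stratified by indication at enrollment (PCI/ACS) and antiplatelet (aspirin/placebo"). The same model serves the non-inferiority test and the superiority step. Protocol 8.4.3.1 specifies the same single stratified model for the hazard ratio, its 95% interval and the p-value.
- **Aspirin versus placebo.** SAP 7.6.2.1 uses a "Cox proportional hazards model including antiplatelet (aspirin/placebo) as a covariate, stratified by indication at enrollment (PCI/ACS) and oral anticoagulant treatment group".
- **Baseline data.** Protocol Table 5.1-1 schedules weight, serum creatinine and "prior VKA use, and CHADS-VASC and HAS-BLED scores" at the screening/randomization visit. Age, weight and creatinine also enter the dosing criteria in Protocol 4.5. All four variables are listed as baseline summaries in SAP 7.3.1.1 and as subgroups in SAP Tables 7.6.1.3 and 7.6.2.2.
- **Where extra terms do appear.** SAP 7.6.1.1 has an anticoagulant-by-antiplatelet interaction model, and the subgroup sections add one grouping variable and its interaction at a time.
- **Power.** Protocol 8.1 claims "at least 77.5% power for superiority test of apixaban versus VKA assuming a risk reduction of 25" per cent. SAP section 5 repeats this at a "two-sided significant level of 0.05"; the synopsis words it as "assuming a risk reduction of 25% and a one-sided significance level of 0.025", which is the same test for this purpose.

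**The concern.** A Cox model that leaves out prognostic baseline variables pulls the treatment log hazard ratio slightly toward zero and so loses some power. The plan measures several plausible bleeding predictors before randomization, and the sponsor itself treats them as relevant enough for dosing criteria and subgroups, but none enters a confirmatory bleeding model.

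Two tests are affected. Superiority of apixaban on bleeding is the second step of the hierarchy in SAP 7.1 and gates both later composites; its stated power is below the 80% that the sample-size adjustment table aims for. Superiority of aspirin placebo over aspirin on bleeding is one of the dual primary objectives. Neither test is judged against a margin, so adjusting them does not touch the 1.2 non-inferiority criterion.

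**Working it through.** **Inputs from the documents** (Protocol 8.1, SAP section 5): 4600 subjects, 1:1; 357 events; VKA risk 9% per half year; superiority effect 25% reduction; non-inferiority margin 1.2 with a 10% reduction assumed; 1% per year lost; one-sided 0.025. **Not in the documents:** the prognostic strength of the baseline variables. This is assumed as C-index 0.60 to 0.75. For a normal risk score, C = Φ(SD/√2), so the SD of the log hazard runs from 0.36 to 0.95.

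**Step 1. Reproduce the stated power.** Power = Φ(√(D/4)·|ln HR| − 1.96).

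- Superiority, D = 357, HR 0.75: √89.25 × 0.2877 = 2.718; 2.718 − 1.96 = 0.758; Φ = 77.6%. The plan states at least 77.5%.
- Non-inferiority, D = 357: the distance is ln(1.2/0.9) = 0.2877, so again 77.6%. The plan states 77%.
- At the adjustment table's 379 events: √94.75 × 0.2877 = 2.800; Φ(0.840) = 80.0%.

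The stated figures hold. The planned rates actually imply slightly more superiority events: 2300 × 0.09 + 2300 × 0.0675 = 362.25. That gives about 78% at HR 0.75. If the hazard ratio is derived from the two risks, it is ln(0.9325)/ln(0.91) = 0.741 and power is about 81%.

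**Step 2. Gain from adjustment.** Paired simulation: 4600 subjects, 9% VKA six-month risk, marginal HR 0.75, 1% per year lost, about 363 events per trial, one normal baseline risk score, with Cox fits with and without the score. There were 8000 trials per row (6000 for the last).

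| Assumed C-index | SD of log hazard | Power unadjusted | Power adjusted | Gain in points (MC SE) | Mean HR, unadjusted to adjusted |
|---|---|---|---|---|---|
| 0.60 | 0.358 | 78.37% | 78.85% | 0.48 (0.18) | 0.7493 to 0.7481 |
| 0.65 | 0.545 | 77.68% | 78.56% | 0.89 (0.22) | 0.7499 to 0.7468 |
| 0.70 | 0.742 | 77.84% | 79.99% | 2.15 (0.27) | 0.7482 to 0.7423 |
| 0.75 | 0.954 | 78.23% | 82.20% | 3.97 (0.35) | 0.7490 to 0.7375 |

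The unadjusted column varies by simulation noise: its standard error is √(0.78 × 0.22/8000), about 0.5 point. The paired gain is the more precise figure. Fixing the conditional rather than the marginal HR at 0.75 (C-index 0.65) gave 76.9% to 77.7%, a gain of 0.8 point. A separate simulation with four covariates entered gave gains of about 0.4, 1.0 and 1.9 points at SD 0.3, 0.5 and 0.7, with the log hazard ratio moving by less than 0.01.

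**Step 3. Put the gain in events.** Inverting the Step 1 formula, D = 4·[(1.96 + z_power)/ln 0.75]². Raising 77.6% by 1 point needs 366 events and by 2 points needs 376. That is 9 to 19 more than 357, against the 22 that separate 357 from 379.

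**Step 4. Effect on non-inferiority.** In a further simulation at a true HR of 1.2, with SD 0.5 and 0.7, the one-sided error was 2.6 to 2.8% unadjusted and 2.4 to 2.5% adjusted. Adjustment would not loosen that test, but the proposal leaves it unadjusted anyway.

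**The case against.** The case for leaving the plan alone is substantial, and much of it stands.

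- **The stated test is valid.** It matches the stratified log-rank basis of the sample size and the model in protocol 8.4.3.1. A reader might infer an analytical error; the documents do not support that.
- **The covariate clause is not empty.** A reader might infer that SAP 7.1 points to nothing. In fact SAP 7.6 describes interaction and subgroup models with extra terms, which can satisfy a permissive clause. Text after SAP 7.6.2.3 is also redacted. What stands is narrower: the readable confirmatory models have no baseline risk term.
- **No fixed loss can be claimed.** A reader might take 1 to 2 points as established. It holds only at an assumed C-index of about 0.65 to 0.70. The main simulation is also favourable: one correctly specified score with no missing data. HAS-BLED may overlap with the other variables, so gains must not be added up.
- **No shortfall is shown for aspirin.** The sub-80% figure is stated only for apixaban versus VKA. The plan gives no power for aspirin versus placebo, so it cannot be called underpowered on this evidence.
- **Baseline data may be incomplete.** The variables are scheduled, not guaranteed. SAP 7.6.1.3 foresees undeterminable values, and SAP 7.6.3.2 and 7.6.3.3 say laboratory data and vital signs are not systematically collected. Even so, creatinine is an eligibility criterion, and the dose-subgroup footnote needs the dose criteria in VKA subjects too.
- **Two models for one endpoint.** Consecutive steps of the hierarchy would use different models, so an adjusted superiority p-value could disagree with the interval used for non-inferiority. This is a real cost and must be acknowledged in the SAP.

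These points narrow the claim and add to its cost. They do not remove a modest gain obtainable from data already scheduled.

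**Conclusion.** The point holds as a cheap improvement of low severity. Both bleeding superiority tests are valid as written but leave baseline prognostic information unused. For apixaban versus VKA at the planned size and HR 0.75, the expected gain is about 0.5 point for weak variables, 1 to 2 points for moderate ones and up to about 4 points at C-index 0.75. This rests on an assumed prognostic strength, an adequately specified model and few missing values. Adjustment for aspirin versus placebo should work in the same direction, but without a stated effect size or power its gain cannot be sized from the documents.

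The possible sample-size increase does not make the point moot: the planned rates average (8.1% + 9%)/2 = 8.55%, while the highest row of the adjustment table is 7.6%, so the table specifies no increase if rates are as planned.

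**What to change.** 1. In SAP 7.6.1.1 (superiority step only) and SAP 7.6.2.1, add baseline age, weight and serum creatinine as continuous terms, and HAS-BLED score, to the stratified Cox model.
2. Fix the functional form and one simple missing-value rule, applied without regard to treatment group, so that no subject drops out of the confirmatory test. The subgroup rule of excluding subjects with undeterminable values should not carry over.
3. Keep the non-inferiority test on the stated stratified model against 1.2; an adjusted version may be reported as supportive.
4. Report the unadjusted superiority result beside the adjusted one, and state in advance that the adjusted p-value decides the superiority step even if the unadjusted interval points the other way.
5. Replace the permissive sentence in SAP 7.1 with the named list. If the sponsor prefers no adjustment, say there that the confirmatory models use treatment and strata only.
6. Align protocol 8.4.3.1, and finalize all of this before unblinding.

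**Cost.** Protocol and SAP wording and a few model terms, with no new data or patients. The superiority hazard ratio becomes conditional on the covariates and may differ slightly from the hazard ratio and interval used for non-inferiority.
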